##### ~~10.3.4.5.6. 10.3.4.10. Allergic/Hypersensitivity Reactions~~

Summaries and listings of allergic and other hypersensitivity AEs including injection site reaction will be provided.

##### ~~10.3.4.6. 10.3.4.11. Immunogenicity~~

Summaries and listings of dulaglutide ADA will be generated.

##### ~~10.3.4.7. 10.3.4.12. Laboratory Analyses~~

Laboratory measurements will be listed by patient. Additional listings will be presented for laboratory measurements that are outside the normal range and for measurements outside certain prespecified clinically relevant thresholds.

##### ~~10.3.4.8. 10.3.4.13. Vital Signs~~

Vital signs will be listed for all randomized patients.

##### ~~10.3.4.9. 10.3.4.14. Electrocardiograms~~

Descriptive statistics for the absolute measurements, outliers, and changes from baseline for selected ECG parameters defined in the SAP, including QT corrected for heart rate using

Fridericia's formula (QTcF) will be presented by treatment and visit. These parameters will be analyzed using a similar MMRM-based model as that described in Section 10.3.1 for continuous variable analysis.

Leo Document ID = 0c4771e4-5f04-410d-ba2c-aa0e2ac98b02

Approver: PPD  
Approval Date & Time: 04-Nov-2016 21:07:21 GMT  
Signature meaning: Approved

Approver: PPD  
Approval Date & Time: 07-Nov-2016 13:52:15 GMT  
Signature meaning: Approved

List of Figures

Figure	Page
Figure GBGJ.1. Illustration of study design for Clinical Protocol H9X-MC-GBGJ.....	13

List of Appendices

Appendix		Page
Appendix 1.	Analysis Windows for the Selected Parameters.....	45

3. Revision History

Statistical analysis plan (SAP) Version 1 was approved prior to unblinding (or the first visit when a subject receives study drug or any other protocol intervention if the clinical trial is open-label).

4. Study Objectives and Endpoints

Table GBGJ.1 shows the objectives and endpoints of the study.

Table GBGJ.1. Objectives and Endpoints

Objectives	Endpoints
Primary To demonstrate that once weekly dulaglutide (4.5 mg, 3.0 mg, 1.5 mg) is superior to placebo in HbA1c reduction at 18 weeks in patients with T2D on concomitant metformin monotherapy.	
 The change in HbA1c from baseline
Secondary Efficacy 
 To compare each dulaglutide arm (4.5 mg, 3.0 mg, 1.5 mg) to the placebo arm at 18 weeks for secondary efficacy parameters 	
 Proportion of patients achieving HbA1c target of <7.0% The change in fasting serum glucose (FSG; central laboratory) from baseline The change in body weight from baseline
Safety 
 To compare each dulaglutide arm (4.5 mg, 3.0 mg, 1.5 mg) to the placebo arm for selected safety parameters at 18 weeks 	
 Treatment-emergent adverse events (TEAEs) and serious adverse events (SAEs) Discontinuation of study drug due to adverse events (AEs) Incidence and rate of hypoglycemia (severe, total, documented symptomatic, and nocturnal)
Pharmacokinetics and Pharmacodynamics 
 To characterize the pharmacokinetics (PK) of dulaglutide and establish the relationships between dose/exposure and key safety and efficacy measures 	
 PK parameters (eg, Cmax, AUC) Pharmacodynamic evaluations will include HbA1c, FSG, body weight, QTcF interval, and heart rate
Tertiary/Exploratory Efficacy 
 To compare each dulaglutide arm (4.5 mg, 3.0 mg, 1.5 mg) to the placebo arm for additional efficacy measures at 18 weeks 	
 Proportion of patients achieving HbA1c target ≤6.5% The change in 6-point self-monitored plasma glucose (SMPG) profiles from baseline The change in fasting plasma glucagon from baseline The change from baseline in insulin resistance (HOMA-IR) and β-cell function (HOMA-%B) as measured by the HOMA2 Method (Caumo et al. 2006)

Objectives and Endpoints

Objectives	Endpoints

Tertiary/Exploratory (continued)
 
Efficacy
 
 • To compare the investigational dose dulaglutide arms (4.5 mg and 3.0 mg) to the 1.5 mg arm for efficacy measures at 18 weeks 
Safety
 
 • To compare the investigational dose dulaglutide arms (4.5 mg and 3.0 mg) to the placebo arm for additional safety measures at 18 weeks • To compare the investigational dose dulaglutide arms (4.5 mg and 3.0 mg) to the 1.5 mg arm for safety measures at 18 weeks 	
 • Change from baseline in HbA1c • Proportion of patients achieving HbA1c target <7.0% or ≤6.5% • The change in FSG (by central laboratory) from baseline • The change in body weight from baseline • The change in 6-point SMPG profiles from baseline • The change in fasting plasma glucagon from baseline • The change in HOMA-IR and HOMA-%B from baseline • Selected gastrointestinal tolerability AEs (nausea, vomiting, and diarrhea) • Pancreatic safety assessed by incidence of cases of adjudicated pancreatitis • CV safety assessed by the incidence of adjudicated deaths and nonfatal major CV events • Thyroid-related safety assessed by the incidence of cases of thyroid neoplasms • Vital signs (PR, BP) • ECG (HR, QTcF, supraventricular arrhythmias and cardiac conduction abnormalities) • Immune system-related safety, including the incidence of dulaglutide antidrug antibodies (ADA) and the incidence of allergic and hypersensitivity reactions • Injection site reactions • Incidence of rescue therapy initiation due to severe, persistent hyperglycemia • TEAEs and SAEs • Discontinuation of study drug due to AEs • Incidence and rate of hypoglycemia (severe, total, documented symptomatic, and nocturnal) • Selected gastrointestinal tolerability AEs (nausea, vomiting, and diarrhea) • Pancreatic safety assessed by incidence of cases of adjudicated pancreatitis • CV safety assessed by the incidence of adjudicated deaths and nonfatal major CV events

Objectives and Endpoints

Objectives	Endpoints
Tertiary/Exploratory (concluded)	
 • Thyroid-related safety assessed by the incidence of cases of thyroid neoplasms • Vital signs (PR, BP) • ECG parameters (HR, QTcF, supraventricular arrhythmias and cardiac conduction abnormalities) • Immune system-related safety, including the incidence of dulaglutide ADA and the incidence of allergic and hypersensitivity reactions • Injection site reactions • Incidence of rescue therapy initiation due to severe, persistent hyperglycemia
Safety	
 • To compare the titration algorithms (Algorithm 1 vs. Algorithm 2) within the investigational dose dulaglutide arms (4.5 mg and 3.0 mg) and across the investigational dose arms versus dulaglutide 1.5 mg and placebo at 6 and 18 weeks • Incidence of selected GI AEs (nausea, vomiting, and diarrhea) • Vital signs (PR, BP)

Abbreviations: ADA = antidrug antibodies; AE = adverse event; AUC = area under concentration-time curve; BP = blood pressure; Cmax = maximum concentration; CV = cardiovascular; ECG = electrocardiogram; FSG = fasting serum glucose; GI = gastrointestinal; HbA1c = hemoglobin A1c; HOMA = Homeostasis Model Assessment; HR = heart rate; PR = pulse rate; QTcF = Fridericia's corrected QT interval; T2D = type 2 diabetes mellitus; SAEs = serious adverse events; SMPG = self-monitored plasma glucose; TEAS = treatment emergent adverse events.

5. Study Design

5.1. Summary of Study Design

Study H9X-MC-GBGJ (GBGJ) is a randomized, multicenter, placebo-controlled, double-blind Phase 2 trial in T2D patients on metformin monotherapy. The study is designed to assess the efficacy and safety of once weekly dulaglutide 3.0 mg and 4.5 mg in comparison to placebo. In addition, the trial will explore how these dulaglutide doses compare to the approved dulaglutide 1.5 mg dose to support dose selection for further development in Phase 3 trials, and to guide design of these additional trials. Study GBGJ will also explore the effect of 2 dulaglutide dose titration algorithms on gastrointestinal (GI) tolerability with investigational doses to guide design of the definitive algorithm to be evaluated in Phase 3 trials. The primary objective of this trial is to show superiority of the 3 dulaglutide doses (4.5 mg, 3.0 mg, 1.5 mg) to placebo in change in hemoglobin A1c (HbA1c) at 18 weeks.

During the trial, an unblinded internal assessment committee (AC) will review data on safety and tolerability in study participants according to a prespecified schedule in order to assure the safety of randomized patients. An efficacy/safety interim analysis will be conducted after approximately 120 patients have completed the 18-week therapy.

The study will consist of 3 periods: an approximately 2-week lead-in period, followed by an 18-week treatment period, and a 4-week safety follow-up period.

Figure [GBGJ.1](#) illustrates the study design.

[figure not shown]

Figure GBGJ.1. Illustration of study design for Clinical Protocol H9X-MC-GBGJ.

5.2. Determination of Sample Size

Assuming a screen failure rate of 30%, approximately 429 patients will need to be screened to attain approximately 300 patients randomized to the 4 treatment arms in a 1:1:1:1 ratio for 4.5 mg, 3.0 mg, 1.5 mg dulaglutide, or placebo weekly (~75 patients per arm). For the investigational dulaglutide dose arms (4.5 mg and 3.0 mg), approximately 38 patients will be assigned to each titration algorithm (Algorithms 1 and 2). Assuming a 20% dropout, this will result in approximately 60 patients per arm and 30 patients per algorithm (in each of the investigational-dose dulaglutide arms) completing the study.

The aforementioned sample size provides $\geq 90\%$ power to demonstrate superiority for the dulaglutide doses (4.5 mg, 3.0 mg, and 1.5 mg) to placebo with respect to HbA1c change from baseline to 18 weeks. This assumes a true glycemic effect difference of -1% HbA1c for each dulaglutide dose versus placebo, and a standard deviation (SD) of 1.2% with a 2-sided alpha of 0.05.

5.3. Method of Assignment to Treatment

Patients who meet all criteria for enrollment will be randomized to one of the study treatment arms at Visit 3. Assignment to treatment arms will be determined by a computer-generated random sequence using an Interactive Web Response System (IWRS). The IWRS will be used

to assign cartons containing double-blinded study drug to each patient. Site personnel will confirm that they have located the correct cartons by entering a confirmation number found on the label into the IWRS.

Block randomization will be used at the country level. Patients will be randomized in a 1:1:1:1 ratio (dulaglutide 4.5 mg, dulaglutide 3.0 mg, dulaglutide 1.5 mg, placebo). Within the dulaglutide 4.5 mg and 3.0 mg arms, patients will be randomly assigned (1:1) to Algorithm 1 or Algorithm 2. Randomization will be stratified by HbA1c (<8%, \geq 8%).

6. A Priori Statistical Methods

6.1. General Considerations

Statistical analysis of this study will be the responsibility of Eli Lilly and Company or its designee. Any change to the data analysis methods described in the protocol will require an amendment ONLY if it changes a principal feature of the protocol. Any other change to the data analysis methods described in the protocol, and the justification for making the change, will be described in the statistical analysis plan (SAP) or the clinical study report (CSR). Additional exploratory analyses of the data may be conducted as deemed appropriate without further changes made to the protocol or SAP even after the datalock.

Countries with fewer than 10 randomized patients will be pooled for statistical analyses. Pooled country will be employed for all formal statistical model-based analyses as a block factor unless otherwise denoted.

Unless otherwise specified, all tests of treatment effects will be conducted at a 2-sided alpha level of 0.05, and confidence intervals (CIs) will be calculated at 95%, 2-sided. All tests of interactions between treatments and factors of interest will be conducted at a 2-sided alpha level of 0.10. No adjustments for multiplicity will be performed.

The baseline visit will be Visit 3. For all variables, including HbA1c, if baseline data are not available or are missing, the last nonmissing measurement taken prior to this visit will be used for the baseline measurement. The efficacy measure for the primary analysis is defined as the change from baseline in HbA1c to Week 18 (Visit 12).

For all statistical analyses, missing data will be treated as missing at random unless otherwise specified; therefore, no imputation is needed unless otherwise stated.

The treatment groups mentioned in this document are based on the randomized treatment groups: dulaglutide 4.5 mg, dulaglutide 3.0 mg, dulaglutide 1.5 mg, placebo. For the purposes of tables, figures, the treatment groups will be: Dula 4.5, Dula 3.0, Dula 1.5, and Placebo. For data listings, the treatment groups will be presented as Placebo, Dula 1.5, Dula 3.0/A1 representing dulaglutide 3.0 mg/algorithm 1, Dula 3.0/A2 representing dulaglutide 3.0 mg/algorithm 2, Dula 4.5/A1 representing dulaglutide 4.5 mg/algorithm 1, Dula 4.5/A2 representing dulaglutide 4.5 mg/algorithm 2.

Incidence of nausea, vomiting, and diarrhea, vital signs (pulse rate, blood pressure [PR, BP]), electrocardiogram (ECG) variables (heart rate [HR], PR interval, and Fridericia's corrected QT interval [QTcF]), and pancreatic enzyme (amylase and lipase) will be summarized by the randomized treatments, and by algorithm within the same investigational dulaglutide dose, and by algorithm across the investigational dulaglutide doses.

Placebo will serve as the reference treatment for each dulaglutide dose, while dulaglutide 1.5 mg as the active comparator for each investigational dulaglutide dose.

All efficacy and safety data will be summarized by each treatment group at each scheduled visit unless otherwise indicated. A scheduled visit is based on the analysis window for the selected

parameters of interest (Appendix 1, Table APP1.1) not the actual visit number reported by the site. For the other measures, the actual scheduled visit reported by the sites will be used.

A mixed-model repeated measures (MMRM) analysis will be used to analyze continuous longitudinal variables. In this model, restricted maximum likelihood will be used to obtain model estimates with Kenward-Roger (KR) option to estimate denominator degrees of freedom. The corresponding baseline value will be used as a covariate, and the stratification factors (pooled country, HbA1c strata [screening HbA1c at Visit 1: <8.0%, \geq 8.0%]), treatment (dulaglutide 4.5 mg, dulaglutide 3.0 mg, dulaglutide 1.5 mg, placebo), visit, and treatment-by-visit interaction will be fixed effects. For HbA1c change from baseline analysis or HbA1c target analysis, HbA1c strata will be replaced with continuous baseline HbA1c as a covariate from the aforementioned model. An unstructured covariance structure will be used to model the within-patient errors. If this model fails to converge, the following covariance structures will be tested in order:

- toeplitz with heterogeneity
- autoregressive with heterogeneity, by visit
- compound symmetry with heterogeneous variances by visit
- toeplitz
- autoregressive
- compound symmetry without heterogeneous variances, by visit
- compound symmetry

The first covariance structure that converges will be used.

The analysis of covariance (ANCOVA) as a sensitivity analysis for the primary and secondary continuous efficacy endpoints using the last observation carried forward (LOCF) described in Section 10.3.1 of the protocol H9X-MC-GBGJ(a) will not be used for analyses of secondary continuous efficacy endpoints as the analysis was shown to produce biased results (Lachin 2016) with little inferential value.

For continuous laboratory measurements for safety, an analysis of variance (ANOVA) on ranks will be used with treatment as a fixed effect.

For all continuous measures, summary statistics will include number of patients, mean, SD, median, minimum, and maximum for both the actual and change from baseline values at each scheduled visit for each treatment unless otherwise specified. Least-squares mean (LS mean) and standard errors (SEs) derived from the model will also be displayed for the change from baseline values at each scheduled visit for each treatment. Treatment comparisons will be displayed showing the treatment difference LS mean and the 95% CIs between each dose and placebo, and between each investigational dulaglutide dose and 1.5 mg at the same visit, along with the corresponding p-values.

Summary statistics for categorical measures will include number of subjects and percentages. The percentage of patients achieving target HbA1c <7.0% at Week 18 will be analyzed using a longitudinal logistic regression with repeated measurements with treatment, visit, treatment-by-visit interaction, and baseline HbA1c-by-visit interaction as fixed effects and baseline HbA1c as a covariate. For the analysis of other categorical measures, Fisher's exact test will be used for treatment comparisons, unless 80% of cells have an expected value of at least 5, in which case the Chi-square test will be used unless otherwise stated. Unless otherwise stated, categorical variables will be summarized by sample size, the number of patients and percentages for each treatment group at each visit.

Imputed data may be applied in model-based data analysis, but will not be used in data listing.

The latter will only present the non-imputed raw data including site reported scheduled, site reported unscheduled, or early termination visit data; however, only scheduled visits for the measure of interest ([Appendix 1](#), Table APP1.1) will be included in the summary table and statistical inference unless otherwise stated.

Additional analyses may be performed even after datalock if deemed needed.

All statistical analyses will be conducted with Statistical Analysis System (SAS) Version 9.4® or higher unless otherwise stated.

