**Number of Patients:**

A total of approximately 300 patients (~75 patients per arm and ~38 per algorithm) will be randomized and approximately 240 are expected to complete the treatment period (~60 per arm and ~30 per algorithm) to show that each dulaglutide dose arm is superior to placebo with at least 90% power. This sample size calculation assumes a treatment difference of 1.0% in HbA1c reduction, standard deviation of 1.2%, and dropout rate of 20%. The screen failure rate is estimated as 30%. Approximately 429 patients will be screened.

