A mixed-model repeated measures (MMRM) analysis will be used to analyze continuous longitudinal variables. In this model, restricted maximum likelihood will be used to obtain model estimates with Kenward-Roger option to estimate denominator degrees of freedom. The corresponding baseline value will be used as a covariate, and the stratification factor (HbA1c <8% or ≥8%), pooled country, treatment, visit, and treatment-by-visit interaction will be fixed effects. For HbA1c change from baseline analysis, stratification factor will be removed from the aforementioned model. An unstructured covariance structure will be used to model the within-patient errors. If this model fails to converge, the following covariance structures will be tested in order:

- Toeplitz with heterogeneity
- autoregressive with heterogeneity, by visit
- compound symmetry with heterogeneous variances by visit
- Toeplitz
- autoregressive
- compound symmetry without heterogeneous variances, by visit.

The first covariance structure that converges will be used.

For continuous laboratory measurements for safety, an analysis of variance (ANOVA) on ranks will be used with treatment as a fixed effect.

For all continuous measures, summary statistics will include number of patients, mean, SD, median, minimum, and maximum for both the actual and change from baseline measurements at each scheduled visit for each treatment. Least-squares mean (LS mean) and standard errors (SEs) derived from the model will also be displayed for the change from baseline measurements at each scheduled visit for each treatment. Treatment comparisons will be displayed showing the treatment difference LS mean and the 95% CIs between each dose and placebo, and between each investigational dose and 1.5 mg at the same visit, along with the corresponding p-values.

Summary statistics for categorical measures will include number of subjects and percentages. The percentage of patients achieving target HbA1c <7.0% at Week 18 will be analyzed using a longitudinal logistic regression with repeated measurements with treatment, visit, treatment-by-visit interaction, and baseline HbA1c-by-visit interaction as fixed effects and baseline HbA1c as a covariate. For the analysis of other categorical measures, Fisher's exact test will be used for treatment comparisons, unless 80% of cells have an expected value of at least 5, in which case the Chi-square test will be used unless otherwise stated.

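### The primary HbA1c model uses one baseline slope for Weeks 6, 10 and 18; a baseline-by-visit term could modestly improve Week 18 precision at almost no cost

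*SAP*

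**What the plan says.** SAP 6.1 specifies the MMRM with this sentence: "The corresponding baseline value will be used as a covariate, and the stratification factors" (pooled country and HbA1c stratum), treatment, visit and treatment-by-visit are the fixed effects. Within-patient covariance is unstructured. For HbA1c change, continuous baseline HbA1c takes the place of the stratum. Protocol 10.3.1 has the same structure: "The corresponding baseline value will be used as a covariate, and the stratification factor" is followed by pooled country, treatment, visit and treatment-by-visit. Neither document lists baseline-by-visit for HbA1c change, and SAP 6.11.1 makes this model the primary analysis. On-treatment HbA1c is scheduled at Weeks 6, 10 and 18 (Protocol Section 2; SAP Appendix 1).

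The baseline effect is handled differently elsewhere:

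- For the <7.0% target, SAP 6.1 lists "baseline HbA1c-by-visit interaction as fixed effects and baseline HbA1c as a covariate", and Protocol 10.3.1 agrees.
- SAP 6.11.3.1 restates that target model as its primary analysis, with baseline HbA1c as a covariate but no interaction with visit.
- The Bayesian ITP model in SAP 6.11.2.3 multiplies the baseline term by a factor that depends on time.

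For sample size, the SAP assumes "a standard deviation (SD) of 1.2% with a 2-sided alpha of 0.05" and states: "This assumes a true glycemic effect difference of -1% HbA1c for each dulaglutide dose versus placebo". It also says: "Assuming a 20% dropout, this will result in approximately 60 patients per arm". The protocol synopsis gives the aim as "to show that each dulaglutide dose arm is superior to placebo with at least 90% power".

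**The concern.** How strongly HbA1c change depends on baseline may grow as the treatment effect builds. Up to Week 6 no patient has received more than 3.0 mg, and Algorithm 2 patients no more than 1.5 mg (Protocol Table GBGJ.2). If the slope does differ by visit, a common slope is a compromise. With unstructured covariance it is weighted toward the less variable visits, so Week 18 could be adjusted with a slope that is too flat. The unexplained part goes into the Week 18 residual and widens the standard error. The primary contrast, and the comparisons with 1.5 mg that inform Phase 3 dose choice, are both at Week 18.

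**Working it through.** **1. The plan's own figure.** With 75 × 0.80 = 60 completers per arm, SE = 1.2 × √(2/60) = 0.219. Power = Φ(1.0/0.219 − 1.96) = Φ(2.60) = 99.5%, which satisfies the stated lower bound of 90%. About 31 per arm would give 90%.

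**2. Does the SAP itself allow a changing slope?** In the ITP model, the ratio of the Week 6 to the Week 18 baseline effect is (1 − e^(6k))/(1 − e^(18k)). For assumed k = −0.1 this is 0.451/0.835 = 54%, and for k = −0.2 it is 0.699/0.973 = 72%. For any negative k it lies between one third and one. The MMRM fixes it at one.

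**3. Size of the loss.** For complete data, Var = (2/n)(σ² + gap² × s_B²), so variance inflation = gap² × s_B²/σ². Here gap is the Week 18 slope minus the fitted common slope. The documents give no baseline SD, slopes by visit or between-visit correlations, so these are assumptions:

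- s_B = 0.8%. The 7.0% to 10.0% entry range would give 3/√12 = 0.87 if uniform.
- σ from 0.9% to 1.2%, the upper value being the planning SD.

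The last column is 120 × inflation, the extra completers in a two-arm contrast that would restore precision.

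| Slope gap | Inflation, σ = 1.2 | Inflation, σ = 0.9 | Completers of about 120 |
|---|---|---|---|
| 0 | 0% | 0% | 0 |
| 0.1 | 0.4% | 0.8% | 0.5–0.9 |
| 0.2 | 1.8% | 3.2% | 2–4 |
| 0.3 | 4.0% | 7.1% | 5–9 |
| 0.37 | 6.1% | 10.8% | 7–13 |
| 0.5 | 11.1% | 19.8% | 13–24 |

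**4. Simulation.** This used four arms, 300 patients, three visits, 20% dropout and unstructured covariance. Baseline SD was 0.6 or 0.9, the correlation parameter 0.6 or 0.8, with 300 runs per scenario. The SE ratio is the common-slope model over the interaction model at Week 18; the last column is its square minus one.

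| Slopes, Weeks 6/10/18 | Gap found | SE ratio | Variance inflation |
|---|---|---|---|
| −0.4/−0.4/−0.4 (equal) | 0 | 1.000 | 0% |
| −0.3/−0.4/−0.5 (mild) | 0.15–0.19 | 1.003–1.012 | 0.7–2.4% |
| −0.2/−0.35/−0.6 (moderate) | 0.29–0.37 | 1.014–1.045 | 2.8–9.2% |
| −0.1/−0.4/−0.8 (extreme) | 0.44–0.60 | 1.04–1.11 | 8–24% |

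Mean estimates agreed to within 0.002% HbA1c. Common-slope power against placebo was at least 99.3% throughout. The simulation omits pooled country, uses a fixed critical value of 1.97 instead of full Kenward-Roger, and assumes Week 22 is not in the model, on which the SAP is silent. In a separate check, dropout after Week 10 depended on observed HbA1c (about 20% on placebo, 8–10% on active; slopes up to the moderate row). The two models' contrasts with placebo differed by at most 0.02% HbA1c.

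**5. Could power fall to 90%?** That needs SE = 1/(1.960 + 1.282) = 0.308, a rise of 0.308/0.219 = 1.41, or 41%. At σ = 1.2 and s_B = 0.8 the gap would have to be 1.2 × √(1.408² − 1)/0.8 = 1.5. Even a gap of 0.5 leaves power at 99.1%.

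**6. Contrasts with 1.5 mg.** Protocol 5.5 looks for about 0.2% additional HbA1c reduction. At SD 1.2 the SE of 0.219 is already that large, and the 95% half-width is 1.96 × 0.219 = 0.43. An 11% variance inflation would widen it to 0.43 × √1.11 = 0.45.

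**The case against.** The common-slope MMRM is a valid prespecified model in an exploratory Phase 2 trial. Any slope misfit goes into the unstructured covariance, so the SE is larger but not falsely small. Randomization stratified at HbA1c 8% already limits chance imbalance. If HbA1c were uniform on 7% to 10%, within-stratum variance would be (1/3)(1/12) + (2/3)(4/12) = 0.25 of a total 0.75, so about two thirds of the imbalance variance is removed. The strata use screening HbA1c, however, and the model SE would not show this gain. Comparisons with 1.5 mg rest mainly on Bayesian probabilities, and the ITP model already has a time-varying baseline effect. The SAP is also not consistent on the <7.0% model, so that comparison supports the point only against SAP 6.1 and Protocol 10.3.1.

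All of this stands, and it limits the size of the point. It does not argue against the term. SAP 6.11.1 still reports MMRM differences from 1.5 mg with intervals and p-values, and SAP 6.16.2.2 sends MMRM results to the Assessment Committee. The fallback Bayesian model in SAP 6.11.2.3 has a single baseline coefficient across visits.

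**Conclusion.** This is a low-severity efficiency and consistency point. The primary HbA1c model has one baseline slope across three visits, and under the stated assumptions this may cost nothing or about 0.4% to 11% in Week 18 variance. The larger losses in the extreme rows need slope differences that nothing in the documents indicates.

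Three stronger readings are tempting, and the documents do not support them:

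- **Precision is certainly lost.** The loss is conditional on slopes differing by visit and is zero if they are equal. No figure in either document places the trial in the range.
- **The Week 18 comparison is biased, or superiority over placebo is at risk.** The randomized contrast is essentially unchanged, and power stays near 99%.
- **The same gain is shown for fasting glucose, weight, ECG, vital signs and pancreatic enzymes.** The calculations concern HbA1c only.

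**What to change.** Before treatment codes are opened for the efficacy interim, add baseline HbA1c-by-visit to the HbA1c change MMRM in SAP 6.1, or state why it is left out. Say also whether Week 22 enters the model. Reconcile SAP 6.1 with SAP 6.11.3.1 so that the <7.0% model is specified one way. The two lists also differ on pooled country, which only 6.11.3.1 names.

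The cost is two extra parameters for three visits with about 300 patients. With equal slopes the simulated SE ratio was 1.000, so the term costs nothing visible if it proves unnecessary. Extension to other endpoints is optional and should be weighed separately. Vital signs, with nine on-treatment visits, would need eight extra parameters in a model that already has six treatment groups.
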